The objective of this study is to assess the feasibility and acceptability of an SSI (i.e., SPYKids) for parents on local Manitoban service and program waitlists who have children with health, behavioural, and developmental needs. This objective will be divided into Primary and Secondary outcomes.

1. Primary Outcomes: [FEASIBILITY & ACCEPTABILITY]:

Primary outcomes are aimed at determining the feasibility and acceptability of SPYKids compared to SAU. This will be done through monitoring of both clinical coach adherence to protocols via a fidelity checklist and parent satisfaction of the overall SSI via feedback questionnaires including both scaled responses and open-ended responses, using both quantitative and qualitative methodology. Parent feedback of the SSI will be assessed using the Program Feedback Scale²⁰ (adapted from [name] research), and the feedback questionnaire, which was created by researchers in the lab for the purposes of this study. Please see the attached Appendix C for all questionnaires.

2. Secondary Outcomes:

Secondary outcomes include metrics of parenting stress and mental health between the SPYKids and SAU groups before and after the SPYKids session. Other exploratory outcomes will include both parent and child well-being.

- Parent well-being: Secondary outcomes related to parent well-being will be changes in parenting stress (Parenting Stress Index²¹) and parent mental health

(Patient Health Questionnaire-9²², Generalized Anxiety Disorder – 7 item scale²³, PROMIS Anger - Short Form²⁴). Exploratory outcomes include changes in hope (Beck Hopelessness Scale-4²⁵), Perceived control/agency²⁶, Readiness to change (Readiness Ruler²⁷), and Problem Solving²⁶.

- Child well-being: Primary analyses will compare changes in child well-being scores (Strengths & Difficulties Questionnaire²⁸) between the SPYKids vs SAU groups. Secondary analyses will examine persistence of these effects at the 3-month follow-up.

Research Methods

Participants

We plan to recruit 70-140 participants and hope to randomize 70 participants to either the SAU or SSI groups (n= 35 per condition). In order to be eligible to participate, they must have a residence in Manitoba, be at least 18 years old, must identify as a primary caregiver to a child who is 2-5 years old, and the child must be on a waitlist for Neurodevelopmental Services in Manitoba (See Eligibility Screener in Appendix C).

Design & Study Procedures

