Across all self-report questionnaire outcomes, measures have excellent reliability and validity. This includes established cut-offs indicating mental health problem severity needs therapeutic services with high sensitivity/specificity to diagnostic interviews. Constructs with established tools from consortium agreements, per the COMET (Core Outcome Measures in Effectiveness Trials) Initiative are prioritized.²⁹

Primary outcome. Child mental health. The primary analyses will compare the change in child mental health symptom scores between (a) the SPYKids vs SAU group at $p=0.05$ using a linear model for the change, accounting for pre-intervention scores and important covariate of child age. Secondary analyses will examine persistence of these effects at the 3-month-follow-up by examining the time-by-intervention interactions in a linear mixed-effects model accounting for within-subject serial correlations, and between-subject effects of the intervention and age.

Secondary outcomes. Parenting stress & mental health. We will use similar linear mixed-effects models for the analysis of key secondary outcomes.

Exploratory outcomes. Parent Self-Efficacy. Exploratory analyses (SPYKids only) will assess the extent to which dimensions of parenting self-efficacy (hope,²⁵ agency,²⁶ readiness to change²⁷) immediately following the intervention are associated with primary and secondary change. This will inform how immediate post-treatment progress is linked to subsequent improvements in well-being. Parent Satisfaction will be assessed to determine if key benchmark

acceptability is met 3.5/5 on an established scale.²⁰ Participants will complete open-ended text-based items allowing them to express their views on the intervention content, their engagement with this content, their satisfaction with their involvement in the intervention, and suggested improvements. Open-ended text items will be analyzed using thematic analysis.³⁰

General considerations. In general, p-values < .05 will be considered statistically significant, without controlling for multiple inference. Complete-case methods will be used for planned analyses; however, sensitivity analyses may be used to examine the impacts of imputation on conclusions, should the usual assumptions appear to be met (MAR, missing at random, or MCAR, missing completely at random). Data will be stored in REDCap following Good Clinical Practices.³¹ Analyses will be done in R v.4.0.0 and the lme4 package v 1.1-26.35

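### Persistence at 3 months rests on unspecified time-by-intervention interactions; name the baseline-adjusted 3-month group difference as the deciding quantity

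*Combined protocol and SAP*

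**What the plan says.** The Aims section (Child well-being) sets the question: "Secondary analyses will examine persistence of these effects at the 3-month follow-up". The Statistical Analyses section (Primary outcome) repeats it and names the tool. The primary comparison is made "using a linear model for the change, accounting for pre-intervention scores and important covariate of child age". Persistence is then assessed "by examining the time-by-intervention interactions in a linear mixed-effects model", "accounting for within-subject serial correlations, and between-subject effects of the intervention and age".

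For parenting stress and parent mental health the plan adds: "We will use similar linear mixed-effects models for the analysis of key secondary outcomes". Under General considerations it states: "In general, p-values < .05 will be considered statistically significant, without controlling for multiple inference".

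The plan does not state:
- whether the pre-intervention score is a response visit or a covariate in the mixed model;
- whether time is categorical or continuous, and which visit is the reference;
- whether one coefficient or a joint test decides;
- any between-group estimate at 3 months, or any criterion for calling an effect persistent.

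**The concern.** Persistence asks whether the arms still differ at 3 months. A time-by-intervention interaction asks whether the group difference changes between visits. The two questions coincide only when the change is measured from baseline, where randomisation makes the expected difference zero, and only when the 3-month term is read alone.

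Under other ordinary ways of fitting the model, the interaction can be significant because of a 2-week effect that has since gone, or null because the effect has held steady. If the choice is left until the data are in, the conclusion about persistence of the child outcome can depend on coding. Anyone who uses the similar models for a 3-month comparison of parent outcomes meets the same ambiguity.

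**Working it through.** **Inputs from the plan.** 35 per arm (Participants); significance level 0.05 (General considerations); outcome visits at baseline, about 2 weeks and 3 months. The plan gives no power calculation, so there is no stated figure to reproduce.

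**Assumptions.** Two-sided test, SD 1, known covariance, no dropout. The effect is 0.5 SD, chosen because the Background describes medium effects of single-session interventions. The plan gives no correlations between visits. Seven sets are used, written as baseline-2 weeks / 2 weeks-3 months / baseline-3 months.

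**Scenarios.** Group differences at the three visits are (0, 0.5, 0.5) if the effect persists and (0, 0.5, 0) if it vanishes.

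**Formula.** For a contrast matrix L with k rows, difference vector δ and visit correlation matrix R, λ = (n/2)·(Lδ)ᵀ(L R Lᵀ)⁻¹(Lδ) with n = 35. The rejection probability is the chance that a noncentral chi-square with k df and noncentrality λ exceeds the 95% point of the central chi-square.

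**Worked case, 0.8/0.6/0.5.**

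1. *Joint 2-df test, three visits.* The changes from baseline have variances 2(1−0.8) = 0.4 and 2(1−0.5) = 1.0, and covariance 1−0.8−0.5+0.6 = 0.3. The determinant is 0.4×1.0−0.3² = 0.31.
   - Vanished: λ = 17.5×0.25×1.0/0.31 = 14.11, rejection 0.93.
   - Persisted: λ = 17.5×0.25×(1.0+0.4−0.6)/0.31 = 11.29, rejection 0.86.
2. *Post-baseline visits only, baseline as covariate with a slope for each visit.* The interaction is the 3-month effect minus the 2-week effect. Its variance factor is 2(1−0.6)−(0.5−0.8)² = 0.71.
   - Persisted: λ = 0, rejection 0.05.
   - Vanished: λ = 17.5×0.25/0.71 = 6.16, rejection 0.70.
3. *Three visits, 3-month-versus-baseline term alone.*
   - Persisted: λ = 17.5×0.25/(2×0.5) = 4.375, power 0.55.
   - Vanished: rejection 0.05.
4. *Baseline-adjusted 3-month difference.*
   - Persisted: λ = 17.5×0.25/(1−0.5²) = 5.83, power 0.68.
   - Vanished: rejection 0.05.

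**All sets.** CS is compound symmetry and AR is AR(1) by visit.

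| Correlations | Joint: vanished | Joint: persisted | Post-only: vanished | Post-only: persisted | 3-month term: persisted | Adjusted contrast: persisted |
|---|---|---|---|---|---|---|
| 0.8/0.6/0.5 | 0.93 | 0.86 | 0.70 | 0.05 | 0.55 | 0.68 |
| 0.7/0.6/0.5 | 0.81 | 0.71 | 0.67 | 0.05 | 0.55 | 0.68 |
| 0.7/0.7/0.6 | 0.85 | 0.73 | 0.78 | 0.05 | 0.65 | 0.74 |
| CS 0.5 | 0.57 | 0.57 | 0.55 | 0.05 | 0.55 | 0.68 |
| AR 0.5 | 0.66 | 0.48 | 0.58 | 0.05 | 0.40 | 0.58 |
| CS 0.7 | 0.80 | 0.80 | 0.77 | 0.05 | 0.77 | 0.83 |
| AR 0.7 | 0.90 | 0.69 | 0.80 | 0.05 | 0.54 | 0.67 |

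The last two quantities reject 0.05 of the time in every set when the effect has vanished. The joint test is never more likely to be significant when the effect persisted than when it vanished. With time linear in months, the slope interaction over the CS and AR sets rejects 0.15-0.50 of the time if the effect persisted and 0.14-0.43 if it vanished, with the sign reversed in the vanished case.

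**The case against.** The strongest reply is that the text, read sympathetically, describes the sound analysis. The mixed-model sentence lists no pre-score covariate although the sentence before it does, and it speaks of interactions in the plural. Both features suggest that baseline is a response visit. With categorical time and baseline as reference, the 3-month interaction term is the group difference in change at 3 months and holds its 5% error rate. This stands. A reader might infer that the planned analysis is wrong, or that it reverses the answer; the documents do not support that, because they name neither a joint test nor a post-baseline-only model, and they admit the valid reading.

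Three further points stand:
- In the post-baseline-only model, 5% rejection under full persistence is simply the correct error rate of a test of change. Setting it against the 68-74% power of the adjusted contrast compares two different questions. The fair comparator for the fix is the 3-month term.
- A reader might infer that false persistence claims are also planned for parenting stress and parent mental health. The plan attaches a persistence aim only to the child outcome and says no more than that similar models will be used for the others.
- This is a pilot with feasibility and acceptability as its stated objective, and persistence is a secondary analysis. The main between-arm comparison is unaffected.

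What does not stand is that nothing needs changing. The deciding term is still unnamed, and even the sound reading uses the baseline score less efficiently than it could.

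**Conclusion.** The concern holds as an unresolved choice of deciding quantity, not as proof that the stated analysis fails. Under a joint three-visit test, significance does not distinguish a persisted effect (48-86% rejection) from a vanished one (57-93%). Under a post-baseline-only model, full persistence is null by construction. Under the valid reading the conclusion is sound, but power is lower than for the adjusted contrast. With correlations 0.8/0.6/0.5 or 0.7/0.6/0.5 it is 0.55 against 0.68, and with 0.7/0.7/0.6 it is 0.65 against 0.74, a difference of roughly 9-13 points.

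These figures rest on the assumed 0.5 SD effect, the assumed correlations, two-sided testing and no dropout. The plan uses complete cases and gives no dropout rate, so actual power would be lower with losses. The difference in what each test addresses does not depend on the assumptions.

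**What to change.** In Statistical Analyses, state that time is categorical and that persistence is the SPYKids-minus-SAU difference in SDQ at 3 months, estimated from the mixed model with adjustment for baseline SDQ and child age, and reported with its 95% CI. Report the 2-week-to-3-month interaction only as a description of how the effect changed. Where the similar models for parenting stress and parent mental health are used for a 3-month comparison, use the same contrast with that measure's own baseline.

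Visit labels should be settled at the same time. The participant contact summary and the Honorarium paragraph disagree on the first SAU follow-up (2 weeks or 1 month) and on whether the SSI group's 3-month visit is counted from the pre-questionnaire or from the session. These passages must be reconciled.

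The contrast itself costs one or two sentences. It needs no extra participants, visits or data.

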diagnosis-specific symptoms, with over 85% of families reporting clinically elevated parenting stress and low child quality of life.^{3,4} Up to 70% of children with NDDs will go on to develop additional mental illness in childhood, further highlighting the importance of early intervention.⁵ Supportive parent-child relationships are critical for promoting resilient long-term development in children with NDDs.^{6,7} Familial influences are particularly pronounced in the first 5 years, when children develop foundational emotional and behavioural regulation skills.⁸ During this time, children benefit greatly from supportive parenting to understand their emotional experiences, learn to cope with distress, and manage impulsivity in prosocial ways.^{9,10} Despite the importance of early intervention for promoting positive mental health, less than 25% of families of children with NDDs receive services.^{11,12} This is due, in part, to lengthy waitlists for initial assessments (up to 1.5 years in Manitoba) and high therapeutic dropout rates, with families attending an average of 3.9 of 16 recommended sessions.^{11,12} There is **immediate and critical need** for novel approaches that provide accessible front-line, timely support to families.

Parent-directed single-session interventions (SSIs) are designed to increase parental ability to understand and address emergent mental health problems. Defined as “specific, structured programs that intentionally involve just one visit or encounter with a provider,” SSIs can teach parents how to support children’s emotional development and impulse control to reduce mental health problems, while reducing high-conflict parenting that can worsen mental health over time. SSIs offer a highly scalable approach, with demonstrated efficacy (medium effects) across a variety of psychiatric concerns.^{13,14} However, they have yet to be adapted to the unique needs of caregivers of preschool-aged children with NDDs.¹⁴ SSIs are evidenced-based as both a stand-alone service and an immediate support complement to waitlists in existing care systems.

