Participant Involvement in Study. For a flowchart of participant contact points please see attachment ‘SPYKids Points of Contact’ in Appendix D. After completing the online eligibility screener, those who are ineligible will also be automatically sent a compassionate email via REDCap informing them that they are not eligible, with a resource list of mental

health, crisis, and parenting resources. Contact information for the research team will also be included should they have any questions regarding eligibility. Participants who are eligible will be informed via REDCap and automatically sent to the pre-questionnaire. Participants will be screened using questions (e.g., “Are you currently on a waitlist for accessing services for your child?”). Please see Appendix C for REDCap the Eligibility Screener.

Quick Summary of Participant Contact Points if eligible (N=70):

1. Participants will read the main program consent form.
2. If they agree to consent, participants will begin the online pre-questionnaires.
3. Following the pre-questionnaires participants will be randomized to either SAU or SSI group via ID# using an online tool (randomizer.org) and will be notified via email of what group they have been randomized to.
4. Participants randomized to the SSI Group (n=35) will take part in the 90-minute SSI via telehealth, the post-questionnaires immediately post intervention and the 2 follow up questionnaires (2 weeks after the SSI and 3 months after the pre-questionnaire) to assess maintenance effects. Immediately following randomization, participants will be sent an email with an invitation to book a time for the SSI using Microsoft Bookings, a University of Manitoba App part of the Microsoft 365 suite of apps. Participants in this group will also receive a follow-up email from the clinical coach 1-week following the SSI.
5. Participants randomized to the SAU group (n=35) will receive services as usual on the SCCY waitlist, as well as receive a list of psychological and family support services. They will also participate in the eligibility screener, pre-questionnaires, the 2-week post questionnaires, and 3-month post follow-up questionnaires.

Further Details on Project Components:

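### The 3-month mixed model, reused for parenting stress and parent mental health, does not say how the pre-intervention score enters or which contrast measures persistence

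*Combined protocol and SAP*

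**What the plan says.** All references are to the combined protocol and SAP.

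- Statistical Analyses, Primary outcome: the change in child mental health is compared between arms "using a linear model for the change, accounting for pre-intervention scores and important covariate of child age".
- Same paragraph, for the 3-month follow-up: persistence is examined by "examining the time-by-intervention interactions in a linear mixed-effects model accounting for within-subject serial correlations, and between-subject effects of the intervention and age". Age carries over from the primary model; the pre-intervention score is not listed.
- Statistical Analyses, Secondary outcomes (parenting stress and mental health): "We will use similar linear mixed-effects models for the analysis of key secondary outcomes". No further terms are given.
- Aims and Hypotheses, Secondary Outcomes: for the child, "Secondary analyses will examine persistence of these effects at the 3-month follow-up". For parents, the comparison is of "metrics of parenting stress and mental health between the SPYKids and SAU groups before and after the SPYKids session".
- Quick Summary of Participant Contact Points: "Following the pre-questionnaires participants will be randomized to either SAU or SSI group". The pre-intervention score is therefore collected before allocation.
- Statistical Analyses, General considerations: "Analyses will be done in R v.4.0.0 and the lme4 package". The coding of time, the random effects and the residual covariance are not stated.

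**The concern.** One sentence governs the 3-month child result and, through the similar models, the between-arm results for parenting stress and parent mental health. It can be fitted in at least three ways.

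- **Baseline as a response with free arm means.** Listing an intervention effect beside the interaction makes this a natural choice. The 3-month contrast is then a difference in raw change, which makes less use of the baseline score than the primary model does.
- **Baseline as a response with arm means constrained equal.** This is as efficient as covariate adjustment.
- **Only the two follow-ups as responses.** The interaction is then the change in effect between the follow-ups, which answers a different question.

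At stake are the width of the 3-month intervals at 35 families per arm and what the word interaction will mean when the result is reported.

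**Working it through.** The documents state no correlation, SD, effect size or power for these outcomes, so there is no plan figure to reproduce.

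**Inputs.** n = 35 per arm (Participants); all families complete; pre-intervention and 3-month scores with equal SD, set to 1; categorical visits. The pre-to-3-month correlation rho is my assumption.

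**Free baseline against adjusted baseline.**
- Difference in raw change: variance (2/n) × 2(1 − rho).
- Baseline-adjusted difference: variance (2/n) × (1 − rho²).
- Ratio: 2(1 − rho)/[(1 − rho)(1 + rho)] = 2/(1 + rho).
- At rho 0.5: (2/35) × 1.00 = 0.0571 against (2/35) × 0.75 = 0.0429, ratio 1.33.

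Half-widths use the t distribution with 66 df. Equivalent n is 35 × (1 + rho)/2.

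| rho (assumed) | Variance ratio | 95% CI half-width, raw change (SD) | Half-width, adjusted (SD) | Equivalent n per arm |
|---|---|---|---|---|
| 0.3 | 1.54 | 0.56 | 0.46 | 22.8 |
| 0.5 | 1.33 | 0.48 | 0.41 | 26.3 |
| 0.6 | 1.25 | 0.43 | 0.38 | 28.0 |
| 0.7 | 1.18 | 0.37 | 0.34 | 29.8 |
| 0.8 | 1.11 | 0.30 | 0.29 | 31.5 |
| 0.9 | 1.05 | 0.21 | 0.21 | 33.3 |

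**Checks.**
- An exact generalised least squares calculation with three visits gives the same ratios. Only the pre-to-3-month correlation matters: decaying patterns with that value at 0.5, 0.6 and 0.64 gave 1.33, 1.25 and 1.22.
- Constraining arm means equal at baseline gives the adjusted variance exactly (ratio 1.00).
- Simulation at 35 per arm, which pays for estimating the baseline slope, gave 1.32, 1.19 and 1.10 at rho 0.5, 0.65 and 0.8.

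**Unequal variances.** With k = baseline SD/3-month SD, the ratio is (k² + 1 − 2·rho·k)/(1 − rho²). At rho 0.7:
- k = 0.8: (0.64 + 1 − 1.12)/0.51 = 1.02.
- k = 1.2: (1.44 + 1 − 1.68)/0.51 = 1.49.

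**Illustrative power.** The Background describes single-session interventions "with demonstrated efficacy (medium effects) across a variety of psychiatric concerns". Taking that as 0.5 SD is my assumption, not a design input. Power is then 54% with raw change and 66% adjusted at rho 0.5, and 90% and 93% at rho 0.8.

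**Only the follow-ups modelled.** Let d1 and d3 be the arm differences at the first follow-up and at 3 months. The interaction is d3 − d1.
- 0.5 SD at both visits gives 0.5 − 0.5 = 0, so the test rejects 5% of the time.
- 0.5 SD lost by 3 months gives −0.5. With a correlation of 0.7 between follow-ups, the SE is √[(2/35) × 0.6] = 0.185 and the test rejects 76% of the time.

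A sustained effect therefore appears as a null interaction and a lost one as a significant interaction. This does not depend on the pre-to-3-month rho.

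**The case against.** The other side has a fair case. Raw change is a valid analysis under randomization, and preferring adjustment is a matter of efficiency. The persistence sentence refers back to the effects just defined, which are baseline-adjusted, so it may be shorthand for an adjusted model. The Aims describe scores before and after the session, which argues against a model of the follow-ups alone. Even in such a model an intervention effect stands beside the interaction, and a sustained benefit would show there. The gain is modest, the figures assume 35 complete families per arm, and the trial's main goals are feasibility and acceptability.

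Most of this stands and limits the point to precision and clarity. It does not remove it: the text does not settle which model will be fitted. A non-significant interaction is also weak evidence of persistence. In the follow-ups-only example its 95% half-width is about 2.0 × 0.185 = 0.37 SD.

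Three stronger readings are tempting and unsupported.

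- **The 3-month result is biased.** Raw and adjusted change target the same effect under randomization.
- **A loss of 11% to 33% is a property of this trial.** It needs an assumed rho, equal variances and categorical visits, none of which the plan gives.
- **The plan will distort the 3-month effect through linear time, or its error rate through a random intercept alone.** The plan states neither; it refers to serial correlation and names the software.

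The questionnaire table and contact flowchart are in appendices not available here, so I assume that each scale is collected before the session and at both follow-ups.

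**Conclusion.** The point holds as under-specification with an avoidable loss of precision. The pre-intervention score is in the primary model and is not listed for the 3-month model or the similar models for the key secondary outcomes. With an unconstrained baseline, the 3-month variance is 2/(1+rho) times the adjusted one under equal variances and categorical visits: 33% to 11% larger for an assumed rho of 0.5 to 0.8, with no loss if baseline means are constrained equal. The ambiguity over what the interaction measures is independent of rho and is reason enough to name the 3-month contrast. These are secondary analyses of a pilot, and the feasibility and acceptability goals are unaffected.

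A separate matter came up in checking the visits. The contact-point summary puts the SAU first follow-up at 2 weeks, while the Honorarium paragraph puts it at 1 month after the pre-questionnaire. The SSI 3-month visit runs from the pre-questionnaire in the former and from the session in the latter. After randomization SAU families complete only the two follow-ups, so the disputed first visit also supplies the earliest between-arm change.

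**What to change.** For the SDQ, Parenting Stress Index, PHQ-9, GAD-7 and PROMIS Anger, state one model.

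- **Responses:** scores at the first follow-up and at 3 months.
- **Fixed effects:** categorical visit, arm, arm-by-visit, baseline score, baseline-by-visit and child age. An equivalent choice is baseline as a response with arm means constrained equal at baseline.
- **Covariance:** visit-specific variances and correlations, for example nlme::gls with corSymm and varIdent.
- **Estimate:** the between-arm difference at 3 months, with its 95% CI, named as the measure of persistence.

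If the present sentence is shorthand for a baseline-adjusted model, a clause saying so settles how baseline enters; the 3-month contrast still has to be named.

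The cost is a few lines of text and one more free R package; no new data are needed. The small downside is the extra covariance parameters: 3 with two follow-ups, 6 if baseline is a response. With complete data the covariate form converged in all 7,500 simulated trials of 35 per arm; it was not tested with missing data.

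Separately, reconcile the contact-point summary and the Honorarium paragraph on the SAU first follow-up and on the origin of the SSI 3-month visit, so that each visit means the same in both arms.

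### The 3-month persistence test is not adjusted for child age or, with the pre score as a response, for the pre-intervention score, so it does not match the primary effect

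*Combined protocol and SAP*

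**What the plan says.** All the model statements are in the combined protocol and SAP, Statistical Analyses.

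- **Primary analysis** (Primary outcome paragraph): the arms are compared "using a linear model for the change, accounting for pre-intervention scores and important covariate of child age". Age and pre score act on the change, so the treatment contrast is adjusted for both.
- **Persistence at 3 months** (same paragraph): this is judged "by examining the time-by-intervention interactions in a linear mixed-effects model", "accounting for within-subject serial correlations, and between-subject effects of the intervention and age". The only interaction named is time-by-intervention. There is no age-by-time term, no model equation, no statement of which visits are responses, and no mention of the pre score as a covariate in this model.
- **Missing data** (General considerations): "Complete-case methods will be used for planned analyses".
- **Design**: 35 per arm are planned, and each participant "must identify as a primary caregiver to a child who is 2-5 years old" (Participants). The SAU arm completes the "pre-questionnaires, the 2-week post questionnaires, and 3-month post follow-up questionnaires" (Quick Summary of Participant Contact Points); the SSI arm also has assessments at these three points.
- **Key secondary outcomes**: similar mixed models are planned for parenting stress and mental health.

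**The concern.** The plan calls child age important and lists it in both models, but it does different work in each. In the change model it adjusts the treatment effect. In the mixed model it raises or lowers all of a child's scores by the same amount, whereas the tested quantity is built from within-child differences.

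The second analysis is meant to show whether the first effect lasts, so the two results will be read side by side. If one is adjusted for pre score and age and the other for neither, part of any apparent fading or persistence can come from the change of model. At 35 per arm, chance differences between arms in age or pre score would also go uncorrected in the 3-month result.

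**Working it through.** The plan states no power, standard deviation, target difference or age-change correlation, so it has no figure to reproduce. The check is structural, followed by a size under stated assumptions.

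**1. Algebra.** For child i in arm g at visit j, let Y_ij = μ_gj + β·age_i + e_ij, with a common covariance over visits and complete data. Generalized least squares gives μ̂_gj = Ȳ_gj − β̂·(mean age in arm g). The age term does not depend on j. The 3-month interaction is therefore

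(μ̂_1,3m − μ̂_1,pre) − (μ̂_0,3m − μ̂_0,pre) = (Ȳ_1,3m − Ȳ_1,pre) − (Ȳ_0,3m − Ȳ_0,pre),

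which is the raw difference in mean change. The cancellation holds for any common serial-correlation structure. With time entered linearly the interaction is a difference in slopes, and age cancels from that too.

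**2. Numerical confirmation.** Simulated trials had 35 per arm, three visits, an assumed correlation of 0.6 between adjacent visits, and assumed age effects on level and change. Over 200 complete-data trials, the interaction with and without the age main effect differed by at most 5.6e-15. A serial-correlation (AR(1)) fit gave −0.542787 both ways for categorical time and −0.271393 both ways for linear time.

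**3. Comparison with the primary-type model.** One simulated dataset, with an age imbalance of 0.5 SD built in:

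| Model for the 3-month effect | Estimate |
|---|---|
| Mixed, no age | −0.644 |
| Mixed, age main effect (as planned) | −0.644 |
| Mixed, age-by-visit | −0.657 |
| Change on arm | −0.644 (SE 0.279) |
| Change on arm and age | −0.657 (SE 0.269) |
| Change on arm and pre score | −0.710 (SE 0.270) |
| Change on arm, pre score and age (primary form) | −0.799 (SE 0.233) |

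The planned model reproduces the unadjusted difference. Adding age-by-visit reproduces change on arm and age, not the primary form.

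**4. Size of the age part.** With age-change correlation r (assumed), the adjusted standard error is √(1−r²) times the unadjusted one. For r = 0.1, 0.2, 0.3 and 0.4 the factors are √0.99 = 0.995, √0.96 = 0.980, √0.91 = 0.954 and √0.84 = 0.917: reductions of 0.5%, 2.0%, 4.6% and 8.3%. A one-standard-error chance imbalance in age is √(2/35) = 0.239 age SD. It shifts the unadjusted contrast by r × 0.239 = 0.024, 0.048, 0.072 and 0.096 SD of change.

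**5. Size of the pre-score part.** In 4,000 simulated trials (35 per arm, assumed within-child correlation 0.6, age-change correlation about 0.22), the standard errors were:

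- no covariate: 0.225
- age: 0.221 (1 − 0.221/0.225 = 1.8% lower)
- pre score: 0.202 (1 − 0.202/0.225 = 10.2% lower)
- both: 0.197 (1 − 0.197/0.225 = 12.4% lower)

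Theory agrees. With equal variances and pre-post correlation ρ, the ratio for the pre score is √((1+ρ)/2) = √0.8 = 0.894 at ρ = 0.6, against 0.202/0.225 = 0.898 simulated.

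**6. Incomplete children kept.** With 20% of post-baseline visits missing and partial records retained, the age main effect moved the interaction only from −0.033 to −0.008 in one dataset and from −0.459 to −0.442 in another. Restricting to children with all visits made the cancellation exact again.

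**The case against.** **The model is not fully specified.** If the responses are only the 2-week and 3-month visits, with the pre score as covariate, the 3-month group contrast is age-adjusted even with a plain age effect (−0.702 without age, −0.772 with age, in the simulated dataset). A reader might infer that no 3-month estimate from such a model could be age-adjusted; the documents do not support that. In this version the interaction asks whether the effect differs between 2 weeks and 3 months, which is a natural meaning of persistence. This stands as a limit. But the plan names the pre score only for the primary model, and the test it names is the interaction, which was 0.270 with and without age even in this version.

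**No validity problem is shown.** A reader might infer an inflated false-positive rate. Given an age imbalance of two standard errors, the rate is P(|N(2r, 1−r²)| > 1.997) = 5.9%, 7.5% or 9.7% for r = 0.2, 0.3 or 0.4. That is conditional on an imbalance of a size expected in roughly 5% of randomizations, and on an assumed correlation. Over all randomizations the unadjusted contrast is unbiased and the error is about 5%.

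**The stakes are modest.** The stated objective is feasibility and acceptability, and this is a secondary analysis with no multiplicity control. Whether age enters as a main effect or by visit is partly a modelling preference. All of this limits the weight of the point. It does not make the two effects comparable.

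**Conclusion.** The point holds. As written, and with complete cases, the listed age covariate does not adjust the tested 3-month effect. With the pre score as a response, that effect is adjusted for neither age nor pre score, while the primary effect is adjusted for both.

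The loss is one of precision, protection against chance imbalance, and consistency, not of validity. Its size rests on correlations absent from the documents. Age alone is worth between nothing and about 8% of the standard error over an assumed correlation of 0 to 0.4. Under the single assumed scenario with within-child correlation 0.6, the pre score is worth about 10%, so the mismatch should not be read as mainly one of age. The cancellation itself needs no such assumption, only that every analysed child has all visits; if partial records are kept, age has a small indirect influence that is still not an adjustment of the change.

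**What to change.** Write out the 3-month model, state which visits are responses, and use one of these:

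1. The primary model applied at 3 months: change from pre to 3 months on intervention, pre score and child age.
2. A mixed model for the post-baseline visits with intervention, visit, intervention-by-visit, and pre score and age each interacted with visit. The 3-month intervention contrast is read from this model.

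With complete data the two give the same 3-month estimate, because in the second each covariate has its own coefficient at each visit.

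Adding only age-by-visit to a model with the pre score as a response is not an equivalent repair. It restores the age adjustment but not the pre-score adjustment. In the 4,000 simulated trials it differed from option 1 by 0.075 SD on average, against 0.038 SD from adding age itself.

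The similar models for parenting stress and mental health should be written out in the same way, since any age term entered there only as a between-subject effect would behave alike.

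The cost is about two degrees of freedom for the first option and a few more for the second. No new data are needed: the pre score is collected, and Data Collection & Management already converts birth dates to age in months. If age is unrelated to change, its inclusion brings no gain.
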